### **8.1.14. Transthyretin**

Blood for serum TTR levels will be collected at scheduled time points before the administration of patisiran. Serum TTR will be assessed using enzyme linked immunosorbent assay (ELISA).

### **8.1.15. Thyroid-Stimulating Hormone**

Blood for TSH levels will be collected at scheduled visits.

### **8.1.16. Vitamin A**

Blood for serum vitamin A levels will be collected at scheduled visits before the administration of vitamin A.

### **8.1.17. Anti-Drug Antibodies**

Serum samples for anti-drug antibodies will be collected as specified in [Table 1](#).

### **8.1.18. Blood Sample for Long-term Storage**

To permit exploratory investigations and the application of novel approaches to bioanalysis that may further elucidate the outcomes of this study, or potentially advance understanding of the safety, mechanism of action and/or efficacy of patisiran, blood samples will be collected for long-term storage. These samples will be securely stored in a central biorepository for up to 10

years following the last patient last visit in this clinical study. After 10 years have elapsed, samples will be destroyed.

Details regarding the collection, processing, storage, and shipping of samples will be provided in the Laboratory Manual.

Exploratory analysis of these biospecimens will be performed by Alnylam Pharmaceuticals or its designees.

All study participants will be advised during the informed consent process of these biobanking details and the potential for exploratory investigation of their samples. Those who do not wish to contribute specimens to the biorepository will be asked to sign an “opt out” form. Moreover, patients who subsequently decide to withdraw consent for the utilization of such stored samples will be able to do so, with the understanding that any data arising from samples already analyzed will be the property of Alnylam Pharmaceuticals.

## 9. ASSESSMENT OF SAFETY

### 9.1. Safety Parameters

All safety assessment measures will be recorded in the patient's medical record and CRF. Refer to [Table 1](#) for the timing of each safety assessment.

#### 9.1.1. Demographic and Medical History

Patient demographic data will be obtained from the parent study.

The Investigator will assess all patients according to the Karnofsky Scale (see [Appendix 1](#)) and the New York Heart Association Classification of Heart Failure (NYHA; see [Appendix 2](#)).

For all patients, a complete medical history will be obtained, including TTR genotype. Any AEs from the parent study that are ongoing on Day 0 will be considered as part of the medical history.

#### 9.1.2. Vital Signs

Vital signs will be measured pre-dose on all dosing days. Vital signs include systolic/diastolic blood pressure, heart rate, respiratory rate, and body temperature, and will be measured in the supine position using an automated instrument after the patient has rested comfortably for 10 minutes. Each patient's blood pressure should be taken using the same arm. Temperature will be recorded in Celsius or Fahrenheit. Heart rate will be counted for a full minute and recorded in beats per minute. Respirations will be counted for a full minute and recorded in breaths per minute.

For the safety of the patient, additional vital signs may be obtained at the discretion of the Investigator.

#### 9.1.3. Weight and Height

Body weight will be measured on all dosing days to inform the next infusion dosing calculation. The rules for using body weight to calculate dose are described in [Section 6.4.2](#).

Height will be measured only if it was not obtained in the parent study.

#### 9.1.4. Physical Examination

A physical examination will be performed by a physician before dosing at scheduled time points. The physical examinations will include the examination of the following: general appearance; head, ears, eyes, nose, and throat; cardiovascular; dermatologic; abdominal; genito-urinary; lymph nodes; hepatic; musculoskeletal; respiratory; and neurological.

#### 9.1.5. Laboratory Assessments

Blood samples for clinical laboratory testing will be collected before patisiran dosing at the time points listed in [Table 1](#). All samples will be sent to a central laboratory for analysis. Details on sample collection, processing, and shipping will be provided in a Laboratory Manual.

In the event of an unexplained clinically relevant abnormal laboratory test occurring after patisiran administration, the test should be repeated and followed up at the discretion of the Investigator until it has returned to the normal range or stabilized, and/or a diagnosis is made to adequately explain the abnormality.

#### **9.1.5.1. Hematology**

Blood samples will be collected for evaluation of the following hematology parameters:

- Hematocrit
- Hemoglobin
- Red blood cell (RBC) count
- White blood cell (WBC) count
- Mean corpuscular volume
- Mean corpuscular hemoglobin
- Mean corpuscular hemoglobin concentration
- Neutrophils, absolute and %
- Lymphocytes, absolute and %
- Monocytes, absolute and %
- Eosinophils, absolute and %
- Basophils, absolute and %
- Platelet count

#### **9.1.5.2. Blood Chemistry**

Blood samples will be collected for evaluation of the following chemistry parameters:

- Aspartate transaminase (AST)
- Alanine transaminase (ALT)
- Sodium
- Potassium
- Blood urea nitrogen (BUN)
- Creatinine
- Alkaline phosphatase
- Bilirubin (total and direct)
- Glucose
- Phosphate
- Albumin
- Calcium

#### **9.1.5.3. Urinalysis**

Urine samples will be collected for evaluation of the following urinalysis parameters:

- Visual inspection for color and appearance
- pH
- Specific gravity
- Ketones
- Protein
- Glucose
- Leukocytes
- Bilirubin
- Nitrite
- Urobilinogen
- Microscopic inspection of sediment

#### **9.1.5.4. Coagulation**

A sample for INR assessment will be collected.

#### **9.1.5.5. Pregnancy Screen**

Urine pregnancy tests are to be performed for all women of child-bearing potential. The timing of the tests is specified in [Table 1](#); additional testing may be done any time pregnancy is suspected.

#### **9.1.6. Ophthalmology Examination**

Ophthalmology examinations will include assessment of visual acuity, visual fields, and slit-lamp evaluation. Visual acuity should be evaluated at the beginning of each specified visit in the study (ie, prior to slit-lamp examination). Manifest refraction will be performed at each specified visit before visual acuity testing and will be used to obtain a correction for visual acuity evaluations. Visual acuity testing should be done with best (most recent) correction.

An electroretinogram (ERG) is a test to evaluate the retinal response to light. It is done to determine if there is damage to rods and cones. ERG testing should be performed if visual changes raise the suspicion for this sort of retinal disease and if clinically indicated.

Further details regarding the ophthalmology examinations will be provided in the Study Reference Manual.

#### **9.1.7. Columbia-Suicide Severity Rating Scale**

The Columbia-Suicide Severity Rating Scale (C-SSRS) will be used to assess each patient's mental status as it relates to suicidal ideation and behavior. If a patient's C-SSRS raises concern of suicidal ideation or behavior, the Investigator must ensure prompt and appropriate mental health interventions in accordance with standard of care.

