### Appendix 6: Familial Amyloidotic Polyneuropathy Stage

Stage	Description
0	No symptoms
I	Unimpaired ambulation; mostly mild sensory, motor, and autonomic neuropathy in the lower limbs
II	Assistance with ambulation required, mostly moderate impairment progression to the lower limbs, upper limbs, and trunk.
III	Wheelchair-bound or bedridden; severe sensory, motor, and autonomic involvement of all limbs.

**ALN-TTR02-006 Protocol Amendment 2****Summary of Changes (dated 05 January 2017)  
compared to Protocol Version 2.1 Taiwan (dated 10 December 2015)****A Multicenter, Open-label, Extension Study to Evaluate the Long-Term Safety and Efficacy of Patisiran in Patients with Familial Amyloidotic Polyneuropathy who have Completed a Prior Clinical Study with Patisiran****Rationale for Protocol Amendment**

The primary purpose of this amendment is to add the Columbia-Suicide Severity Rating Scale (C-SSRS) to the study assessments, which was inadvertently left out of previous versions of the protocol. The inclusion of the C-SSRS addresses a regulatory requirement to prospectively assess suicidality in clinical trials involving all drugs for neurological indications. Overall, this amendment includes the following changes:

- The Columbia-Suicide Severity Rating Scale has been added as an assessment of suicidal ideation and behavior.
- Country-specific versions of the protocol have been integrated in order to increase consistency in the execution of the clinical study globally
- Electroretinograms are now recommended to be performed in the case of suspected retinal disease.
- The premedication regimen has been updated to align with commercially available doses.
- Blood samples for long-term storage have been added in order to permit future exploratory investigations.
- During scheduled phone contact, clinical sites may now ask patients who are receiving home infusions about their general experience receiving these infusions

A detailed summary of the above changes, in addition to changes made for clarity, is provided in [Table 1](#). Corrections to abbreviations, typographical errors and formatting are not detailed.

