**Table 1: Protocol Amendment 2 Detailed Summary of Changes**

The primary section(s) of the protocol affected by the changes in the protocol amendment are indicated. The corresponding text has been revised throughout the protocol. Deleted text is indicated by ~~strikeout~~; added text is indicated by **bold** font.

*Purpose: Added Columbia-Suicide Severity Rating Scale to the study assessments*

The primary change occurs in Table 1 Schedule of Assessments

Added text: Added row to Schedule of Assessments indicating that the Columbia-Suicide Severity Rating Scale is to be collected at 26 weeks and 52 weeks after baseline and annually thereafter, as well as at the End of Study and Early Withdrawal visits.

Section(s) also containing this change or similar changes:

- Synopsis, Criteria for Evaluation, Safety
- Section 9.1.7 Columbia-Suicide Severity Rating Scale (*section added*)

*Purpose: As part of global protocol integration, specified that home infusions are allowed only where applicable country and local regulations allow.*

The primary change occurs in Section 3.1 Overall Study Design

Added text: After the Day 0 visit, patients should return to the clinical site for patisiran dosing once every 21 ( $\pm 3$ ) days, ~~or~~. **Where applicable country and local regulations allow, patients may** receive the patisiran infusions at home by a healthcare professional trained on the protocol and delivery of premedications and patisiran.

Section(s) also containing this change or similar changes:

- Synopsis, Methodology
- Table 1, Schedule of Assessments
- Section 5.3 Treatment Compliance
- Section 6.4.2 Study Drug Administration

*Purpose: As part of global protocol integration, specified that MR neurography is only to be conducted in Germany and France*

The primary change occurs in Table 1 Schedule of Assessments, footnote s

Now reads: ~~Required only for~~ **MR neurography will only be conducted at sites in Germany and France. In these countries, neurography may be conducted for patients who had MR neurography in the parent study and may be imaged for consenting for a subset of patients providing informed consent** who did not have MR neurography previously in their parent study. **Patients who had imaging in the parent study should have Day 0 imaging if they did not undergo MR neurography within the past 3 months.**

Section(s) also containing this change or similar changes:

- Synopsis, Criteria for evaluation, Efficacy

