**Table 1 Schedule of Assessments**

	Day 0 Visit	12 Week Visit	26 Week Visit	52 Week Visit	Annual Visit	End of Study	Early Withdrawal Visit
	Window ≤45 Days from Last Dose a	±4 Weeks	±4 Weeks	±4 Weeks	±6 Weeks	4 (+1) Weeks from Last Dose	4 (+1) Weeks from Last Dose
Procedure							
Informed Consent	X						
Inclusion/Exclusion Criteria	X						
Medical History	X b						
Demographics	X c						
Physical Examination	X d			X	X	X o	X o
Weight	X Prior to Each Dose					X o	X o
mBMI e	X d			X	X	X o	X o
Height	X c						
FAP Stage and PND Score	X d			X	X	X o	X o
Karnofsky Performance Status	X						
NYHA Classification	X			X			[X] f
Vital Signs g	X Prior to Each Dose						
Safety Laboratory Assessments h	X d	X	X	X	X	X	X
INR	X						
Pregnancy Test (urine)	X i		X	X	X	X	X
C-SSRS Questionnaire			X	X	X	X	X

	Day 0 Visit	12 Week Visit	26 Week Visit	52 Week Visit	Annual Visit	End of Study	Early Withdrawal Visit
	Window	≤45 Days from Last Dose a	±4 Weeks	±4 Weeks	±4 Weeks	±6 Weeks	4 (+1) Weeks from Last Dose
Procedure							
TTR Protein (ELISA)	X d		X	X	X	X	X
TSH and Vitamin A				X	X	X o	X o
Blood Sample for Long-term Storage	X	X	X	X	X	X	X
mNIS+7 j	X d			X			[X] f
NIS+7 k	X d			X			[X] f
NIS only					X l	X m	X m
Grip Strength Test n	X d			X			[X] f
10-Meter Walk Test p	X d			X			[X] f
Ophthalmology Examination q	X d			X	X	X o	X o
Skin Punch Biopsy (IENFD and SGNFD) r				X	X	X o	X o
MR Neurography s ( Germany & France only )	X		X	X	X	X o	X o
Pharmacoeconomics Questionnaire	X			X	X	X o	X o
Norfolk QOL-DN t	X d			X	X	X o	X o
COMPASS 31 Questionnaire	X d			X			[X] f
R-ODS Disability	X d			X			[X] f
EQ-5D QOL	X d			X	X	X o	X o
Echocardiogram	X d,u			X			[X] f
Troponin I and NT-proBNP	X d			X			[X] f

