**Table 1 Footnotes:**

Abbreviations: C-SSRS = Columbia-Suicide Severity Rating Scale; COMPASS 31 = Composite Autonomic Symptom Score; ELISA = enzyme linked immunosorbent assay; EQ-5D QOL = EuroQOL; FAP = familial amyloidotic polyneuropathy; IENFD = intraepidermal nerve fiber density; mBMI = modified body mass index; mNIS = Modified Neuropathy Impairment Score; MR = magnetic resonance; NIS = Neuropathy Impairment Score; NT-proBNP = N-terminal prohormone of B-type natriuretic peptide; NYHA = New York Heart Association; PND = polyneuropathy disability; QOL-DN = Quality of Life-Diabetic Neuropathy; R-ODS = Rasch-built Overall Disability Scale; SGNFD = sweat gland nerve fiber density; TSH = thyroid stimulating hormone; TTR = transthyretin

- Every effort should be made to perform Day 0 visit 3 weeks (±3 days) from the last dose of study drug in the parent study. However, the Day 0 visit may occur within 45 days after the last dose in the parent study. Exceptions may be made for medical or regulatory considerations only after consultation with the Medical Monitor.
- Medical history includes TTR genotype. Ongoing AEs from the parent study will be captured as Medical History on the case report form (CRF). Similarly concomitant medications that continue from the parent study will be entered into the database.
- Assessment does not need to be repeated. Information will be obtained from parent study.
- Assessment/procedure does not need to be repeated if performed during the parent study within 45 days of first dose in this study.
- mBMI will be calculated within the clinical database; this calculation does not need to be performed at the study center.
- Assessment/procedure required only if patient withdraws before the 52-week visit.
- Vital signs include blood pressure, heart rate, body temperature, and respiratory rate. Collected supine using an automated instrument after patient rests for 10 minutes. Must be performed pre-dose.
- Includes serum chemistry, hematology, and urinalysis. Refer to Section 9.1.5 for specific laboratory assessments.
- Assessment does not need to be repeated if the patient had a negative pregnancy test (urine or serum) within 14 days of the first dose.

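### The C-SSRS is not scheduled at Day 0 or Week 12, and no rule specific to the scale brings in a parent-study value, so a positive Week 26 result may have no earlier value to compare with

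*Protocol*

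**What the plan says.** Section 9.1.7 opens "The Columbia-Suicide Severity Rating Scale (C-SSRS) will be used to assess each" patient for suicidal ideation and behaviour. It then requires the investigator to act if the result raises concern. It states no visit, no recall period and no baseline rule.

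The timing is in Table 1. The row "C-SSRS Questionnaire" is empty under Day 0 and Week 12 and marked at Week 26, Week 52, Annual, End of Study and Early Withdrawal. The Summary of Changes for Amendment 2 (05 January 2017), which introduced the row, describes the same schedule in words: the scale is "collected at 26 weeks and 52 weeks after baseline and annually thereafter", and also at the two closing visits. The blank cells are therefore deliberate and not a fault of table extraction.

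The rationale for that amendment says that including the scale "addresses a regulatory requirement to prospectively assess suicidality in clinical trials".

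Many other Table 1 rows, such as mNIS+7, the safety laboratory tests and serum TTR, have a Day 0 entry with footnote d: "Assessment/procedure does not need to be repeated if performed during the parent study within 45 days of first dose in this study". The C-SSRS row has neither a Day 0 entry nor this footnote. Section 3.1 has a general rule that the last testing visit of the parent study is the baseline, unless more than 45 days have passed, in which case the baseline tests are repeated on Day 0.

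**The concern.** This is a single-arm study, so a safety finding on a rating scale is read mainly against the same patient's earlier value. If the first value comes about half a year into treatment, a positive answer cannot be set against the patient's state at entry on the same instrument. Section 9.5 makes that comparison matter. A condition present at entry is not reported as an adverse event unless it deteriorates, so classifying a positive Week 26 result needs some knowledge of the state at entry.

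The second issue is timing. The action in section 9.1.7 depends on a C-SSRS result. While no C-SSRS is scheduled, that route is closed, even for a patient who already has ideation on entry.

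Both are matters of data collection. An analysis plan cannot supply a value that was never collected.

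**Working it through.** The plan gives no figure for this, and no power or sample-size calculation bears on it. The check is a reading of the schedule and a dose count.

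**Time to the first scheduled C-SSRS.** Inputs: Week 26 visit, window ±4 weeks (Table 1); one dose every 21 days from Day 0 (section 3.1).

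- Nominal: 26 × 7 = day 182.
- Window: (26 − 4) × 7 = day 154 to (26 + 4) × 7 = day 210, that is, Weeks 22 to 30.

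**Doses given before it**, on the nominal schedule of days 0, 21, 42 and so on, ignoring the ±3-day dosing window and missed doses:

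- Before day 154: days 0 to 147, so 147/21 + 1 = 8 doses.
- Before day 182: days 0 to 168, so 168/21 + 1 = 9 doses.
- Before day 210: days 0 to 189, so 189/21 + 1 = 10 doses.

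**The same count if the scale were also given at Week 12.** Nominal day 12 × 7 = 84. Doses on days 0, 21, 42 and 63 come before it, so 4 doses instead of 9.

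**Is there a route to an earlier value?**

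- *In this study:* only through an Early Withdrawal visit, for a patient who leaves before Week 26.
- *From the parent study:* section 3.1 could supply one, but only if the parent study used the scale, which this document does not say. If more than 45 days had passed, section 3.1 calls for repeat baseline tests on Day 0, and Table 1 has no Day 0 cell for the C-SSRS.

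**Who would gain a pre-drug value from a Day 0 entry?** Section 1.3 admits former placebo patients, for whom Day 0 is the first patisiran dose. Section 3.1 also admits patients from ALN-TTR02-003, and former active-arm patients enter from ALN-TTR02-004. For these two groups Day 0 is a baseline for the extension only.

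**Patients already enrolled.** The first protocol release was 06 November 2014 and the scale was added on 05 January 2017. Patients past Week 26 by then would meet it first at Week 52 or an annual visit. Their number is not given. Section 1.2 still describes the Phase 3 parent study as ongoing, so further Day 0 visits could be expected.

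**The case against.** A reader might infer that this study cannot distinguish ideation or behaviour that began on treatment from what was there before, and that nothing is assessed prospectively in the first half-year. The documents do not support either statement, for these reasons.

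- A blank Day 0 cell does not by itself mean there is no baseline. Skin biopsy also has no Day 0 entry and no footnote d, yet section 10.2.3 plans changes from baseline for the nerve fibre densities. The general rule in section 3.1 may be meant to cover such cases. If the parent studies collected the C-SSRS, former placebo patients have a pre-drug value.
- Section 9.1.7 fixes no recall period, so it cannot be asserted that a Week 26 answer mixes pre-study history with later events.
- Adverse events are monitored continuously with onset dates, patients are asked about changes in health since the last visit, and section 9.1.1 requires a complete medical history. The first half-year lacks a scheduled C-SSRS; it does not lack safety monitoring.
- The amendment refers to prospective assessment and does not say that a baseline is required, so there is no formal contradiction.

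All of this stands and limits the point. It leaves three things untouched. The schedule gives no in-study reference. No rule specific to the scale imports one. Adverse event questioning was already in place when the sponsor decided that a structured scale was needed.

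**Conclusion.** The point holds as a cheap, worthwhile improvement. It is not an error that undermines the study. Table 1 schedules no C-SSRS at Day 0 or Week 12, and the first scheduled administration falls at Weeks 22 to 30, after 8 to 10 nominal doses (9 at the nominal visit). The loss of a comparison value is conditional: it applies unless the parent studies used the scale, in which case section 3.1 would make the last parent-study visit the baseline. The delay before a scheduled C-SSRS can trigger the section 9.1.7 response does not depend on that assumption. A Day 0 value would be a pre-patisiran baseline only for former placebo patients. The reading is of version 3.1 United Kingdom, in the one part of the document that is shown; a later version could differ.

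**What to change.** In Table 1:

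1. Add the C-SSRS at Day 0, before the first dose, and attach footnote d so that a parent-study value within 45 days of the first dose can serve.
2. Add it at the existing Week 12 visit. A Day 0 entry alone would leave the first on-treatment value at Week 26.
3. For patients already past Day 0, record at the first administration any history before Day 0 separately from events since Day 0.

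State in section 9.1.7 that Day 0 is a pre-patisiran reference for former placebo patients and an extension baseline for all others.

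The cost is one short questionnaire at one or two visits that patients already attend. The same amendment added a storage blood sample at both Day 0 and Week 12, so additions at those visits were workable. The remaining weakness is that history for patients already enrolled rests on recall.

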### **9.2. Adverse Events and Serious Adverse Events**

#### **9.2.1. Definition of Adverse Events**

##### **9.2.1.1. Adverse Event**

An AE is any untoward medical occurrence in a patient or clinical investigational patient administered a pharmaceutical product and which does not necessarily have a causal relationship with this treatment.

An AE can therefore be any unfavorable and unintended sign (including an abnormal laboratory finding, for example), symptom, or disease temporally associated with the use of a medicinal product, whether or not considered related to the medicinal product.

Disease progression (including worsening of neuropathy impairment) will not be considered an AE.

All IRRs will be recorded as AEs.

